5.3.6 Assessment of adverse events

5.3.6.1 Definitions of AEs

Adverse event

An adverse event (AE) is defined as any untoward medical occurrence in a patient or clinical investigation subject administered a medicinal product and which does not necessarily have to have a causal relationship with this treatment.

An AE can therefore be any unfavourable and unintended sign (including an abnormal laboratory finding), symptom, or disease temporally associated with the use of a medicinal product, whether or not considered related to the medicinal product.

Serious adverse event

A serious adverse event (SAE) is defined as any AE which:

- results in death,
- is life-threatening,
- requires inpatient hospitalisation or prolongation of existing hospitalisation,
- results in persistent or significant disability or incapacity,
- is a congenital anomaly/birth defect,
- or
- is to be deemed serious for any other reason if it is an important medical event when based upon appropriate medical judgment which may jeopardize the patient and may require medical or surgical intervention to prevent one of the other outcomes listed in the above definitions.

Life-threatening in this context refers to an event in which the patient was at risk of death at the time of the event; it does not refer to an event that hypothetically might have caused death if more severe.

Every new occurrence of cancer must be reported as a serious event regardless of the duration between discontinuation of the drug and the occurrence of the cancer.

AEs considered "Always Serious"

In accordance with the European Medicines Agency initiative on Important Medical Events, Boehringer Ingelheim has set up a list of AEs, which by their nature, can always be

considered to be “serious” even though they may not have met the criteria of an SAE as given above.

The latest list of “Always Serious AEs” can be found in the RDC. These events should always be reported as SAEs.

Adverse events of special interest (AESIs)

The term AESI relates to any specific AE that has been identified at the project level as being of particular concern for prospective safety monitoring and safety assessment within this trial, e.g. the potential for AEs based on knowledge from other compounds in the same class. AESI need to be reported to the Sponsor’s Pharmacovigilance Department within the same timeframe that applies to SAE, see [Section 5.3.7](#).

The following are considered as AESIs:

Hepatic injury

A hepatic injury is defined by the following alterations of hepatic laboratory parameters:

- an elevation of AST and/or ALT ≥ 3 fold ULN combined with an elevation of total bilirubin ≥ 2 fold ULN measured in the same blood draw sample, and/or
- marked peak aminotransferase (ALT, and/or AST) elevations ≥ 10 fold ULN

These lab findings constitute a hepatic injury alert and the patients showing these lab abnormalities need to be followed up according to the “DILI checklist” provided in the ISF and the RDC-system.

In case of clinical symptoms of hepatic injury (icterus, unexplained encephalopathy, unexplained coagulopathy, right upper quadrant abdominal pain, etc.) without lab results (ALT, AST, total bilirubin) available, the investigator should make sure these parameters are analysed, if necessary in an unscheduled blood test. Should the results meet the criteria of hepatic injury alert, the procedures described in the DILI checklist should be followed.

Intensity of AEs

The intensity grading of AEs will be performed according to Rheumatology Common Toxicity Criteria (RCTC) Version 2.0 developed by OMERACT ([R13-3515](#)). Refer to the ISF for intensity/severity classification. Intensity options are:

- Grade 1 mild
- Grade 2 moderate
- Grade 3 severe
- Grade 4 life threatening

Causal relationship of AEs

Medical judgment should be used to determine the relationship, considering all relevant factors, including pattern of reaction, temporal relationship, de-challenge or re-challenge, confounding factors such as concomitant medication, concomitant diseases and relevant history.

Yes: There is a reasonable causal relationship between the trial medication administered and the AE.

No: There is no reasonable causal relationship between the trial medication administered and the AE.

5.3.7 Adverse event collection and reporting

AE Collection

The following must be collected and documented on the eCRF by the Investigator (see [Figure 5.3.7: 1](#))

- From signing the informed consent onwards through the Residual Effect Period (REP), until individual patient's end of trial; all AEs (serious and non-serious) and all AESIs must be collected
- After the individual patient's end of trial: the investigator does not need to actively monitor the patient for AEs but should only report relevant SAEs and relevant AESIs of which the investigator may become aware of.

[figure not shown]

Figure: 5.3.7: 1 Adverse Events Collection

The REP is defined as 15 weeks after the last administration of BI 655066 (active or placebo). All AEs which occurred through the treatment phase and throughout the REP will be considered as on treatment; please see [Section 7.3.4](#). Events which occurred after the REP will be considered as post treatment events.

AE reporting to sponsor and timelines

The Investigator must report SAEs, AESIs, and non-serious AEs which are relevant for the reported SAE or AESI, on the BI SAE form via fax immediately (within 24 hours) to the Sponsor's unique entry point (country specific contact details will be provided in the ISF).

The same timeline applies if follow-up information becomes available. In specific occasions the Investigator could inform the Sponsor upfront via telephone. This does not replace the requirement to complete and fax the BI SAE form.

With receipt of any further information to these events, a follow-up SAE form has to be provided. For follow-up information the same rules and timeline apply as for initial information.

Information required

For each AE, the Investigator should provide the information requested on the appropriate eCRF pages and the BI SAE form, e.g. onset, end date, intensity, treatment required, outcome, seriousness, and action taken with the investigational drug(s). The Investigator should determine the causal relationship to the trial medication.

The following should also be recorded as an (S)AE in the eCRF and SAE form (if applicable):

- Worsening of the underlying disease or of other pre-existing conditions
- Changes in vital signs, ECG, physical examination and laboratory test results, if they are judged clinically relevant by the Investigator.

If such abnormalities already pre-exist prior trial inclusion they will be considered as baseline conditions.

All (S)AEs, including those persisting after individual patient's end of trial must be followed up until they have resolved, have been sufficiently characterized, or no further information can be obtained.

Pregnancy

In the rare case that a female subject participating in this clinical trial becomes pregnant after having taken trial medication, the Investigator must report immediately (within 24 hours) the drug exposure during pregnancy (DEDP) to the Sponsor's unique entry point (country-specific contact details will be provided in the ISF). The Pregnancy Monitoring Form for Clinical Trials (Part A) should be used.

The outcome of the pregnancy associated with the drug exposure during pregnancy must be followed up and reported to the Sponsor's unique entry point on the Pregnancy Monitoring Form for Clinical Trials (Part B).

As pregnancy itself is not to be reported as an AE, in the absence of an accompanying SAE/AESI, only the Pregnancy Monitoring Form for Clinical Trials and not the SAE form is to be completed. If there is an SAE/AESI associated with the pregnancy then the SAE/AESI has to be reported on the SAE form in addition.

If a patient becomes pregnant during a trial, the study medication needs to be discontinued, and the patient will complete end of treatment as well as follow-up procedures.

The ISF will contain the Pregnancy Monitoring Form for Clinical Trials (Part A and B

5.4 DRUG CONCENTRATION MEASUREMENTS AND PHARMACOKINETICS

5.4.1 Assessment of Pharmacokinetics

BI 655066 concentrations will be reported descriptively. No PK parameters will be calculated. PK data will be incorporated into a larger pharmacometric analysis with other trials of BI 655066 project. The relationship between PK and selected efficacy endpoints, biomarkers and AEs may be assessed. PK and demographic data together with treatment assignments and dosing information may be made available to individuals outside of the trial team for the purpose of PK dataset generation in accordance with sponsor's standard procedures.

Refer to [Flow Chart](#) for the time points of PK and ADA sample collection. Date and exact time of drug administration and PK and ADA sampling will be recorded on eCRFs. These actual administration and sampling times will be used for determination of PK parameters. On visits with study medication dosing, PK and ADA sampling should be collected prior to administration of study drug.

After completion of the study (i.e., clinical trial report archived), PK and ADA plasma samples may be used for further methodological investigations (e.g., stability testing).

5.4.2 Methods of sample collection

5.4.2.1 Plasma sampling for pharmacokinetic analysis

For quantification of BI 655066 plasma concentrations, approximately 2.5 mL of blood will be taken at the time points listed in the [Flow Chart](#) under PK sampling.

Detailed instructions for pharmacokinetic sampling, handling, and shipment of plasma samples are provided in the laboratory manual.

5.4.2.2 Plasma sampling for ADA

For ADA assessment, approximately 2.5 mL of blood will be taken at the time points listed in the [Flow Chart](#) under ADA assessment.

Detailed instructions for ADA sampling, handling, and shipment of plasma samples are provided in the laboratory manual.

5.4.3 Analytical determinations

BI 655066 concentrations will be determined by a validated Enzyme Linked Immunosorbent Assay (ELISA).

The presence of ADA to BI 655066 will be assessed via a tiered approach using a validated electrochemiluminescence assay (screening, confirmatory, and titration analysis as appropriate). Samples that are confirmed positive may be further characterized in a validated neutralizing antibody (NAb) assay.

5.5 ASSESSMENT OF EXPLORATORY BIOMARKERS

5.5.1 Skin biopsy assessment

Skin biopsies will be collected in a subset of patients at selected study sites to assess changes in gene and protein expression levels over time by treatment group. Biopsies are planned to be collected from approximately 75 patients. The biomarkers planned to be assessed by immunohistochemistry may include but not be limited to K16, Ki67 (on keratinocytes), S100 A7 (on keratinocytes), lipocalin-2 (NGAL), β -defensin 2, CD3+ T lymphocytes, CD11+ and DC lamp (Dendritic Cells). Dermal and epidermal tissue will be evaluated. In addition, in situ hybridization analyses to identify changes in the proportion of select T cell sub-populations will be determined using expression of specific biomarkers (ie IL-23R on T17 cells and Fox P3 on T reg cells). RNA sequencing profiling of the skin biopsies will also be assessed to link changes in select pathways associated with IL-23 blockade and changes in the T cell sub-populations.

5.5.1.1 Methods of sample collection

Skin biopsies will be performed at time points outlined in the [Flow Chart](#) and should be collected prior to administration of study drug at dosing visits. Participation of patients in skin biopsies requires their separate informed consent. At Visit 2 both non-lesional and lesional skin biopsies will be collected and at Visit 7 only lesional skin biopsies will be collected. Refer to ISF (Laboratory Manual) for biopsy, sample preparation and shipment instructions.

5.5.1.2 Analytical determinations

Immunohistochemistry will be performed as described in [Section 5.5.1](#). RNA will be extracted from skin biopsies according to standard molecular genetics methods and analysed by RNA sequencing, TaqMan[®] or other standard gene expression technologies.

5.5.2 Assessment of soluble protein biomarkers

Serum will be collected pre and post treatment with BI 655066 to assess changes in protein levels of disease specific markers such as but not limited to β -defensin 2, neutrophil gelatinase associated lipocalin-2 (NGAL) and S-100 A8 protein over time by treatment group. Additionally, changes in levels of biomarkers related to metabolic syndrome such as leptin, resistin, TNF α , IL-6 and VEGF will be explored.

5.5.2.1 Methods of sample collection

Approximately 12.5 ml of blood will be collected at time points indicated in the [Flow Chart](#). Samples should be collected prior to administration of study drug at dosing visits. For details on sample handling and logistics refer to the ISF (Laboratory Manual).

5.5.2.2 Analytical determinations

These biomarkers are considered exploratory and respective assays will need to be qualified to meet the required performance criteria.

5.5.3 Biomarker sample banking

After completion of the study any unused serum and tissue samples collected for biomarker sampling as listed in [Section 5.5.1](#) and [5.5.2](#) may be used for further investigations (e.g. additional biomarkers for immunological & inflammatory diseases), if participation and the informed consent for biomarker sample banking is agreed upon by the patient.

Declination to allow storage and use of these samples will not preclude participation in this study. The study samples will be stored for a maximum period of 15 years (under consideration of local legislation and if consented by the patient) upon archiving of the final study report after study completion.

5.5.4 DNA Banking

Participation in the DNA banking sampling is voluntary and not a prerequisite for participation in the trial. The patient must provide informed consent for participation in this optional testing prior to any blood sampling used for DNA banking. The DNA banking sample will be stored in accordance with local ethical and regulatory requirements.

5.5.4.1 Methods of sample collection

One blood sample for DNA banking will be taken at Visit 2. A maximum of 8.5 mL blood will be collected per PaxGene DNA blood sampling tube. For details on sample handling and logistics refer to the ISF (Laboratory Manual).

5.5.4.2 Analytical determinations

The DNA banking sample, derived from the original blood sample, will be stored at AbbVie or a third party delegate (e.g. Boehringer Ingelheim Pharma GmbH & Co.KG; [name]). The stored DNA may be retrospectively analysed, e.g. to identify whether there are other genetic factors that could contribute to a better therapeutic outcome or a higher risk of developing treatment-related adverse drug reactions.

5.6 OTHER ASSESSMENTS

5.6.1 Quality of Life Questionnaires DLQI and WLQ

Dermatology Life Quality Index (DLQI) and Work Limitations Questionnaire (WLQ) are questionnaires self-administered by patients at Visits 2, 8 and EOT. DLQI and WLQ will be used to assess quality of life, overall health and disability status, as well as work limitations (see [Appendix 10.6](#) and [10.7](#)).

5.6.2 Study drug self-administration questionnaire

At study visits with self-administration of BI 655066 drug (active or placebo) by patients the trial site completes a questionnaire. This occurs at Visits 5, 8, 9, 11 and 12. The questionnaire captures information whether the patient did the injections of BI 655066 drug (active or placebo) correctly or not (see [Appendix 10.8](#)).

5.6.3 Health Care Resource Utilization (HCRU) Questionnaire

For the purpose of a separate health economic analysis (such as cost-utility analysis), HCRU data will be collected at visits shown in the [Flow Chart](#). Resource use data collected for calculating direct costs will include hospitalisations, unscheduled outpatient or home visits and emergency room visits. The economic evaluation of the HCRU data will not be part of the Clinical Trial Report, but reported separately.

5.7 APPROPRIATENESS OF MEASUREMENTS

All measurements performed during this trial are standard measurements in psoriasis treatment trials and will be performed in order to monitor safety aspects or assess treatment response in an appropriate way.

Therefore, the appropriateness of all measurements applied in this trial is given.

Information about race should be obtained from all study participants as allowed by local regulations. This is because the prevalence and characteristics of psoriasis differ widely between patients of different racial origin. It will thus be worthwhile to assess if patients of different race will respond differently to the study treatment.

6. INVESTIGATIONAL PLAN

6.1 VISIT SCHEDULE

All patients are to adhere to the visit schedule as specified in the [Flow Chart](#). Each visit date (with its window) is to be counted from Day 1 (randomization). If any visit has to be rescheduled, subsequent visits should follow the original visit date schedule from Day 1. Additional visits for the purpose of re-testing of laboratory parameters or AE monitoring may be included as deemed necessary by the investigator.

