For analysis in each Part (A or B), the Rx Day is calculated relative to the first dose of study drug in the specific study Part. For analysis across Part A and Part B, the Rx days are calculated relative to the date of first dose of study drug injection in Part A.

Definition of Analysis Windows

All time points and corresponding time windows are defined based on Rx Days.

For efficacy analyses, local tolerability, laboratory parameters, and vital sign variables, analysis windows are constructed using the following algorithm:

- Determine the nominal Rx day for each visit (e.g., Week 4 [4 weeks after Baseline visit] equals Rx Day 29).
- In order to include all post baseline data, the first post-baseline interval starts on the first day after the first dose of study drug (Rx Day 2).
- Determine the window around a specific nominal Rx day by adding or subtracting half of the interval between adjacent visits (e.g., days between Week 2 and Week 4 is 14). The threshold between adjacent visits is determined by splitting the interval evenly between the visits. If the resulting split is between Rx days, then the threshold is determined as the midpoint between the adjacent visits. If the resulting split is on an Rx day, then the threshold is determined as being between that Rx day and the Rx day prior to it (e.g., the split between Week 2 and Week 4 would be between Rx Days 22 and 23).
- If more than one assessment is included in a time window the assessment closest to the nominal day will be used. If there are two observations equidistant to the nominal day, the one after the nominal day will be used in analyses. If more than one assessment is included on the same day, then the worst assessment on that day will be used in analyses, except those specified in Section 11.0.

The protocol specified visits and corresponding time windows used in the efficacy analyses, local tolerability, ECG, laboratory parameters, and vital sign variables, are presented in the following tables.

Table 4. Visit Windows for PASI/sPGA and Vital Signs for Part A (ITT_A/PP_A/Safety_A Populations)

Window Label	Target Day	Time Window
Baseline	1	$\leq 1^a$
Week 4	29	[2, 43]
Week 8	57	[44, 71]
Week 12	85	[72, 99]
Week 16	113	[100, 127 ^b]

Rx Day calculated relative to the first dose of study drug. For subjects randomized but not dosed, Rx Day calculated relative to randomization.

- a. If time is collected in vital signs, restrict to records prior to the first dose of study drug.

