- b. The minimum of upper bound and first dose date of study drug on or after Week 16 (and within 105 days of last dose for safety analyses). If time is collected in vital signs, restrict to records prior to the first dose of study drug on or after Week 16.

Table 5. Visit Windows for Laboratory and ECG Parameters for Part A (Safety_A Population)

Window Label	Target Day	Time Window
Baseline	1	≤ 1
Week 4	29	[2, 71]
Week 16	113	[72, 155 ^a]

Rx Day calculated relative to the first dose date of study drug. For subjects randomized but not dosed, Rx Day calculated relative to randomization.

- a. The minimum of upper bound and first dose date/time on or after Week 16 (and within 105 days of last dose for safety analyses).

Table 6. Visit Windows for Other Efficacy Endpoints Only Collected at Week 16 in Part A (ITT_A Population)

Window Label	Target Day	Time Window
Baseline	1	≤ 1
Week 16	113	[2, 225 ^a]

Rx Day calculated relative to the first dose date of study drug. For subjects randomized but not dosed, Rx Day calculated relative to randomization.

- a. The minimum of upper bound and first dose date of study drug on or after Week 16.

Table 7. Visit Windows for Local Tolerability for Part A (Safety_A Population)

Window Label	Target Day	Time Window
Week 1	8	[2,15]
Week 3	22	[16, 25]
Week 4	29	[26, 71]
Week 16	113	[72, 155 ^a]

Rx Day calculated relative to the first dose of study drug. For subjects randomized but not dosed, Rx Day calculated relative to randomization.

- a. The minimum of upper bound and first dose date of study drug on or after Week 16 (and within 105 days of last dose for safety analyses) (and within 105 days of last dose for safety analyses). If time is collected in vital signs, restrict to records prior to the first dose of study drug on or after Week 16.

Table 8. Visit Windows for Analysis of PASI and sPGA in Part B (ITT_B_RR/ITT_B_R/ITT_B_NR/ITT_B_RZB/PP_B_RR Populations)

Window Label	Target Day	Time Window
Entry of B	1	≤ 1
Week 20	29	[2, 43]
Week 24	57	[44, 71]
Week 28	85	[72, 99]
Week 32	113	[100, 127]
Week 36	141	[128, 155]
Week 40	169	[156, 183]
Week 44	197	[184, 211]

Rx Day calculated relative to the first dose of study drug in Part B. For subjects re-randomized but not dosed in Part B, Rx Day calculated relative to the IRT date of re-randomization evaluation.

Table 9. Visit Windows for Laboratory and ECG Parameters for Part B (Safety_B_RR Population)

Window Label	Target Day	Time Window
Entry of B	1	≤ 1
Week 28	85	[2, 141]

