Week 24	169	[156, 183]
Week 28	197	[184, 211]
Week 32	225	[212, 239]
Week 36	253	[240, 267]
Week 40	281	[268, 295]
Week 44	309	[296, 323]
Week 48 (EOT + 4 Weeks)	337	[324, 351 ^b]

Rx Day calculated relative to the first dose of risankizumab.

- a. If time is collected in vital signs, restrict to records prior to the first dose of risankizumab.
- b. The minimum of upper bound and 105 days of last dose of risankizumab for safety analyses.

Table 15. Visit Windows for Local Tolerability Parameters for ALL_RZB Population

Window Label	Target Day	Time Window
Week 1	8	[2, 15]
Week 3	22	[16, 25]
Week 4	29	[26, 71]
Week 16	113	[72, 155]
Week 28	197	[156, 253]
Week 44	309	[254, 323 ^a]

Rx Day calculated relative to the first dose of risankizumab.

- a. The minimum of upper bound and 105 days of last dose of risankizumab for safety analyses.

The time windows specified below will be used for the summary of study drug injections of each period.

Table 16. Visit Windows for Summary of RZB Injections for Part A

Window Label	Target Day	Time Window
Week 0	1	≤ 1
Week 4	29	[2, 57 ^a]

Rx Day calculated relative to the first dose of study drug.

a. Before the first dose on or after Week 16.

Table 17. Visit Windows for Summary of RZB Self-Administration Questionnaire in Part A

Window Label	Target Day	Time Window
Week 4	29	[2, 57 ^a]

Rx Day calculated relative to the first dose of study drug.

a. Before the first dose on or after Week 16.

Table 18. Visit Windows for Summary of RZB Injections for Part B and RZB Self-Administration Questionnaire

Window Label	Target Day	Time Window
Week 16	1	≤ 1
Week 20	29	[2, 57]
Week 28	85	[58, 99]
Week 32	113	[100, 127]

Rx Day calculated relative to the first dose of study drug in Part B.

Table 19. Visit Windows for Summary of ADA Injections for Part A

Window Label	Target Day	Time Window
Week 0	1	≤ 1
Week 1	8	[2, 15]
Week 3	22	[16, 29]
Week 5	36	[30, 43]
Week 7	50	[44, 57]
Week 9	64	[58, 71]
Week 11	78	[72, 85]
Week 13	92	[86, 99]
Week 15	106	[100, 113]

Rx Day calculated relative to the first dose of study drug.

Table 20. Visit Windows for Summary of ADA Injections for Part B

Window Label	Target Day	Time Window
Week 17	8	[1, 15]
Week 19	22	[16, 29]
Week 21	36	[30, 43]
Week 23	50	[44, 57]
Week 25	64	[58, 71]
Week 27	78	[72, 85]
Week 29	92	[86, 99]
Week 31	106	[100, 113]
Week 33	120	[114, 127]
Week 35	134	[128, 141]
Week 37	148	[142, 155]
Week 39	162	[156, 169]
Week 41	176	[170, 183]

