10.1.4 Missing Data Imputations

Missing data will be imputed using the following methods for the efficacy analyses:

- Non-Responder Imputation (NRI): the NRI analysis will categorize any subject who has a missing value at a specific visit as a non-responder for that visit. The only exception is when the subject is a responder both before and after this specific visit window, within the same analysis period, then the subject will be categorized as a responder for the visit. The NRI will be the primary approach in the analyses of categorical variables.
- Last Observation Carried Forward (LOCF): The LOCF analyses will use the completed evaluation from the previous visit within the particular analysis period for efficacy measures assessed to impute missing data at later visits in the same analysis period. Baseline efficacy evaluations will not be carried forward. Of note, post-baseline observations from Part A can be carried

forward to the ITT_B_RZB subjects since treatment is the same. LOCF will be the primary approach in the analyses of continuous variables, and the secondary approach in the analyses of categorical variables.

- As-Observed Cases (OC): The as-observed analysis will not impute values for missing evaluations, and thus a subject who does not have an evaluation on a scheduled visit will be excluded from the as-observed analysis for that visit. As-observed analysis will be the secondary approach in the analysis of continuous variables.
- Multiple Imputation (MI): The MI analysis will be used as sensitivity approach to impute missing data in primary and ranked secondary endpoints. The variables to be included in the imputation model are listed below. If MI is not applicable due to the nature of our data (e.g., MCMC algorithm does not converge), logistic regression or mixed effect model repeat measurement (MMRM) methods will be applied as sensitivity approach, whichever applicable.

The Multiple Imputation analysis will be carried out in three steps.

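### Part B PASI windows run from the Visit 8 dose but visits run from Day 1, so after a very late Visit 8 an in-window Week 44 PASI can be scored as a failure

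*Protocol*

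**What the plan says.** **Visit dates.** Protocol 6.1 counts each visit and its window from Day 1, and a late visit does not move later ones: "If any visit has to be rescheduled, subsequent visits should follow the original visit date schedule from Day 1". The Flow Chart puts Week 40 (Visit 14) at Day 281 and Week 44 (EOT) at Day 309, each ±3 days. Table 4.1.4: 1 allows Visit 8 with the Week 16 treatment decision up to Day 126. Beyond that the patient stays on the previous treatment. Protocol 4.1.4 describes late visits as rare.

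**Analysis windows.** SAP Table 8 sets the Part B PASI/sPGA windows on a different clock: "Rx Day calculated relative to the first dose of study drug in Part B". Week 40 is Rx Days 156-183 (target 169) and Week 44 is Rx Days 184-211 (target 197). Two other tables show that this clock starts at the Visit 8 injection. The table headed "Visit Windows for Summary of RZB Injections for Part B and RZB Self-Administration Questionnaire" places the Week 16 injection at Rx Day 1, and the one headed "Visit Windows for Summary of ADA Injections for Part B" gives Week 17 a target of Rx Day 8.

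**Missing data.** In SAP 10.1.4, "the NRI analysis will categorize any subject who has a missing value at a specific visit as a non-responder for that visit". The one exception requires a response both before and after the empty window. NRI is the primary approach for categorical endpoints. SAP 10.2 makes Week 44 PASI 90 in re-randomised patients the primary endpoint of Part B.

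**The concern.** A late Visit 8 starts the SAP's Part B clock late but leaves the protocol's EOT date unchanged, so the two drift apart by the length of the delay. With enough delay, an EOT visit that is on time by the protocol falls before the Week 44 window opens.

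Nothing in the SAP recovers it. All windows are defined by Rx Day, so the nominal visit label plays no part. The closest-to-target rule works only among assessments already in the same window. The NRI exception cannot apply, because no PASI is scheduled after EOT. A patient seen to be a PASI 90 responder at the Week 44 visit would then count as a non-responder in the Part B primary analysis. The Part B ranked secondary endpoint (PASI 100) and the two sPGA Week 44 endpoints use the same row.

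The SAP also treats this visit differently elsewhere. Table 11 gives other efficacy endpoints collected at Week 44 a window of Rx Days 2-393, and Table 9 gives laboratory and ECG data Rx Days 142-211. On Rx Days 181-183 the same EOT visit would supply Week 44 values for those measures but not for PASI.

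**Working it through.** **Inputs.** EOT on Days 306-312 (Flow Chart, Day 309 ±3). Visit 8 on Days 110-126 (Day 113 - 3 up to the Table 4.1.4: 1 limit). Windows from SAP Table 8. Planning figures of 120 re-randomised patients and PASI 90 rates of 70% and 40% (Protocol 7.7, SAP 4.3).

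**Step 1: reproduce the plan's boundary.** The midpoint of the Week 40 and Week 44 targets is (169 + 197)/2 = 183. Table 8 closes Week 40 at 183 and opens Week 44 at 184. This matches the SAP's worked example, in which "the split between Week 2 and Week 4 would be between Rx Days 22 and 23". It does not match the worded rule, under which, for a split falling on an Rx day, "the threshold is determined as being between that Rx day and the Rx day prior to it"; that would open Week 44 at Rx Day 183. Both readings are carried below.

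**Step 2: find the affected day pairs.** Rx Day = EOT day - Visit 8 day + 1.

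| Visit 8 day | EOT day | Rx Day | Table 8 as printed | Worded split rule |
|---|---|---|---|---|
| 124 | 306 | 183 | Week 40 | Week 44 |
| 125 | 306 | 182 | Week 40 | Week 40 |
| 125 | 307 | 183 | Week 40 | Week 44 |
| 126 | 306 | 181 | Week 40 | Week 40 |
| 126 | 307 | 182 | Week 40 | Week 40 |
| 126 | 308 | 183 | Week 40 | Week 44 |

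Of the 17 × 7 = 119 combinations, these six fail under the printed table and three under the worded rule. With Visit 8 on Day 123 the earliest in-window EOT gives 306 - 123 + 1 = 184, so no in-window EOT fails. An EOT on Day 309 or later is always classified correctly.

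**Step 3: size.** The documents give no late-visit rate. Assume 1-5% of the 120 patients (1.2-6) have Visit 8 on Days 124-126, spread evenly over those days, and that EOT is spread evenly over Days 306-312. There are then 3 × 7 = 21 equally likely pairs. The mean planned response rate over two equal arms is (0.40 + 0.70)/2 = 0.55.

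| | Printed Table 8 | Worded rule |
|---|---|---|
| Share of pairs failing | 6/21 = 29% | 3/21 = 14% |
| Patients affected (1.2-6 × share) | 0.34-1.71 | 0.17-0.86 |
| Responders lost (× 0.55) | 0.19-0.94 | 0.09-0.47 |
| Points lost from the 30-point difference (1-5% × share × 30) | 0.09-0.43 | 0.04-0.21 |

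On power, 60 per arm at 70% vs 40% gives 92.1%. If one, two or three of the 120 patients were affected, in proportion across arms, it would be 91.5%, 91.0% or 90.5%.

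**Step 4: the LOCF sensitivity analysis.** LOCF fills Week 44 with the Week 40 value. Which visit supplies that value depends on closeness to Rx Day 169, with the tie rule "If there are two observations equidistant to the nominal day, the one after the nominal day will be used in analyses". Crossing the six printed pairs with Visit 14 on Days 278-284 gives 6 × 7 = 42 combinations. The EOT visit supplies the Week 40 value in 1, 3, 2, 5, 4 and 3 of 7, in table order, a total of 18 (43%). In the other 24 (57%) the Visit 14 value stands in for the observed EOT value. LOCF therefore does not force a failure, but it often drops the real assessment.

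**The case against.** **The dose anchor is defensible.** Part B asks what 28 weeks of treatment achieves after the switch, and time from the first Part B dose measures that. At Rx Days 181-182 the assessment is nearer the Week 40 target (12-13 days away) than the Week 44 target (15-16 days); at Rx Day 183 it is equidistant. This stands as a reason to keep dose-anchored windows in general. It does not justify treating a scheduled, completed final assessment as missing, particularly as later dosing visits and EOT also follow the Day 1 calendar.

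**The effect is immaterial.** It needs a Visit 8 that is 11-13 days late and an EOT that is 1-3 days early. This stands and sets the severity.

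**The size rests on unsupported assumptions.** This also stands. The 5% upper figure would put that many patients in a three-day band well outside the regular ±3-day window. Even timing and an in-window EOT for every such patient, with no dropout, are conveniences. The ranges are illustrative only.

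**Multiple imputation is also planned.** SAP 10.1.4 plans it for the primary and ranked secondary endpoints, and it would impute the empty Week 44 value instead of fixing it at failure. It is a sensitivity analysis, so the primary NRI result is unchanged.

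**The remedy is partial.** A Visit 8 on Day 123 with an EOT on Day 305, one day outside the window, gives Rx Day 183 and still fails. That is correct. The remedy protects only assessments made within the protocol's own EOT window.

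**Conclusion.** The concern holds. Under Table 8 as printed, six permitted Visit 8/EOT day pairs send an in-window Week 44 PASI to Week 40, and the primary NRI analysis then scores the patient a non-responder whatever was observed. Under the worded split rule there are three such pairs. This assumes the first Part B dose is given at Visit 8, as scheduled; a later first dose would enlarge the shift.

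The practical effect is small: under one responder lost over both arms even in the upper scenario. The rate is not expected to differ by arm, because Visit 8 timing precedes re-randomisation and EOT timing is blinded. The result is a slight dilution of the difference, which would not plausibly alter the Part B conclusion. It is a minor point, worth fixing because the fix is nearly free.

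**What to change.** Add one rule under SAP Table 8: a scheduled Week 44 EOT PASI/sPGA assessment made on Day 309 ±3 from randomisation is used as Week 44 and does not compete for the Week 40 window. Early-termination EOT visits outside those days keep the existing windows. The rule gives the same result under either reading of the split rule.

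The cost is one sentence, with no new data and no protocol change; the SAP is to be signed off before database lock, so the rule can be prespecified. There are two downsides. In the affected cases Week 44 would be 180-182 days after the first Part B dose (306 - 126 = 180; 306 - 124 = 182) instead of the nominal 197 - 1 = 196. The same shift in earlier Table 8 rows, which serve only further endpoints, is left uncorrected.
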